### 4.3. Secondary Outcomes

The effect of treatment (lactose versus maltodextrin co-ingestion on:

- 1) Postprandial de novo lipogenesis (DNL), using heavy water
- 2) Dietary fat oxidation, using a stable isotope-labelled palmitate

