### Laboratory trial days

On the evening before trial days, a 5-mL blood sample will be taken (via venepuncture) for analysis of baseline H enrichment of the body water pool. Participants will then consume a standardised meal with 3 g·kg body water  of H2O for the assessment of fasting hepatic DNL. Participants will continue to consume H2O throughout trial days for the measurement of postprandial DNL.

On postprandial study days, participants will arrive at the laboratories in a rested, overnight fasted state, after 24-hours of diet and physical activity standardisation.

Body mass will first be recorded, and then a cannula will be inserted retrograde into a pre-heated dorsal hand vein for arterialised blood sampling, and baseline blood and expired breath samples will be taken for analysis of plasma metabolite and hormone concentrations, plasma tracer enrichments, and indirect calorimetry, respectively. Participants will then consume a high-fat test drink containing 50 g of fat, plus 100 g of either **lactose**, **sucrose or maltodextrin (Table 1)**. The test drink will also contain 200 mg [U-C]palmitate in order to trace the fate of the dietary fat. This quantity of lactose is roughly equivalent to 400 mL of milk and 400 g plain yoghurt, which is very high but not supraphysiological in light of typical UK intakes.

Table 1. Main laboratory trials and drink composition.

| Trial        | Carbohydrate type mixed with fat source (100 g)      | Fat Source
(50 g)                |
|--------------|--|-------------------------------------|
| Maltodextrin | Glucose polymer; a common sugar substitute (control) | 30 g palm oil and
20 g olive oil |
| Lactose      | Galactose-glucose disaccharide (intervention)        | 30 g palm oil and
20 g olive oil |
| Sucrose      | Fructose-glucose disaccharide (active comparator)    | 30 g palm oil and
20 g olive oil |

Low-calorie-sweetened chocolate flavouring will be added to all drinks.

Participants will be advised that dairy products are used in this study and people following a vegan diet may therefore choose not to participate.

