#### Fasting and postprandial *de novo* lipogenesis

S

Postprandial DNL will be determined by the incorporation of deuterium from  $^2H_2O$  in plasma water into VLDL-TG palmitate using gas chromatography-mass spectrometry (Finnigan GasBench II Thermo Fisher Scientific, Paisley, U.K.) with monitoring ions with mass-to-charge ratios of 270 (M+0) and 271 (M+1) as we have previously performed. In this respect, DNL refers to the proportion of newly synthesized palmitate in VLDL-TG, and this represents the synthesis of fatty acids from non-lipid precursors. The benefit of this method over tracing labelled lactose is that labelling the ingested sugar only captures the conversion of that specific precursor to fatty acids. The  $^2H_2O$  method on the other hand, captures DNL from all precursors. Therefore, if lactose ingestion stimulates the conversion of lactate, galactose and glucose to lipid, this would be captured by our proposed method, but would be partially missed if using lactose labelling.

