#### Primary analyses

Summary statistics (e.g. iAUC, AUC, peak concentrations) will be analysed by one-way ANOVA. Time-course data will be assessed by a two-way (time x treatment) ANOVA. Paired t-tests will be used for post-hoc comparisons, which will be corrected for multiple comparisons using the Holm-Bonferonni adjustment.

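### The DNL secondary outcome has no stated summary or time point and makes no use of the same-visit fasting DNL that the trial collects

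*Combined protocol and SAP*

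**What the plan says.** All references are to the combined protocol and SAP.

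- **Outcome.** Section 4.3 names "Postprandial de novo lipogenesis (DNL), using heavy water", compared between lactose and maltodextrin. It gives no time point and does not say whether the quantity is a single value, an AUC, an iAUC or a change. Section 4.4 repeats postprandial DNL, equally undefined, for the treatment-by-sex interaction.
- **Labelling.** Under Laboratory trial days (section 4.8), heavy water is first taken the evening before, "for the assessment of fasting hepatic DNL", and intake continues "throughout trial days for the measurement of postprandial DNL".
- **Samples.** The evening sample taken before the label serves to measure baseline deuterium "enrichment of the body water pool"; it is not a fasting DNL value. The fasted sample on the trial morning is taken for, among other things, "plasma tracer enrichments, and indirect calorimetry, respectively", so a fasting DNL value can be obtained from it.
- **Measure.** Section 4.9 has a heading that covers both fasting and postprandial DNL, but its text describes only the postprandial one: "DNL refers to the proportion of newly synthesized palmitate in VLDL-TG". No subtraction of, or adjustment for, the fasting value is described.
- **Analysis.** Section 4.11 states "Summary statistics (e.g. iAUC, AUC, peak concentrations) will be analysed by one-way ANOVA" and "Time-course data will be assessed by a two-way (time x treatment) ANOVA". Neither sentence mentions DNL, and no baseline covariate appears anywhere in 4.11.

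**The concern.** Research objective 2 asks what lactose does to fatty acid synthesis in the liver. Because labelling begins the night before, VLDL-TG palmitate may already carry label when the drink is swallowed. A postprandial proportion then combines synthesis the drink could have influenced with synthesis it could not.

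The trial plans the measurement that would help separate the two, but the outcome and analysis text do not take it up. By contrast, the primary outcome and 11 of the 13 outcomes listed in 4.4 are iAUCs, which are referenced to baseline by construction. DNL is not described that way.

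Two things are at stake. The absolute postprandial level cannot be read purely as a response to the drink, and the between-drink comparison may be less precise than the collected data allow. In addition, with the summary undefined, a raw value, an AUC, an iAUC, a change and a time course all remain open for the first-listed secondary outcome until the data are in hand.

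**Working it through.** **The plan's own figure.** Section 4.10 gives power 0.94 for n = 24, d = 0.75 and α = 0.05. A two-sided paired t-test (23 df, noncentrality 0.75 × √24 = 3.674) gives 0.940, so the figure reproduces. It concerns triglyceride iAUC. The documents give no effect size, SD or power for DNL, so what follows is illustrative.

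**Inputs.** n = 24 completers in a crossover (4.10). Assumed: r, the correlation across visits within a person between fasting and postprandial DNL; equal within-person SDs for the two; equal expected fasting values before each drink.

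**Variance relative to the unadjusted postprandial value.**
- Fasting value as covariate: 1 − r²
- Simple change from fasting: 2(1 − r)

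The number of participants an unadjusted analysis would need to match 24 analysed with the covariate is 24/(1 − r²).

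| r | Covariate: variance ratio | Reduction | Unadjusted n for equal precision | Change: variance ratio |
|---|---|---|---|---|
| 0.3 | 0.91 | 9% | 24/0.91 = 26.4 | 1.40 |
| 0.5 | 0.75 | 25% | 24/0.75 = 32.0 | 1.00 |
| 0.7 | 0.51 | 49% | 24/0.51 = 47.1 | 0.60 |

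Change from fasting breaks even where 2(1 − r) = 1, that is at r = 0.5. Below that it is less precise than ignoring the fasting value.

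**What this means for power.** Assume a paired effect of d = 0.5 on the unadjusted value, n = 24 and two-sided α = 0.05. The effective d is 0.5/√(1 − r²) with the covariate and 0.5/√(2(1 − r)) for change; the lost degree of freedom is ignored.

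| r | Unadjusted | Covariate | Change |
|---|---|---|---|
| 0 | 0.65 | 0.65 | 0.38 |
| 0.3 | 0.65 | 0.69 | 0.51 |
| 0.5 | 0.65 | 0.77 | 0.65 |
| 0.7 | 0.65 | 0.91 | 0.86 |

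**Is the contrast biased?** A simulation of 20,000 trials of 24 people at each of r = 0, 0.5 and 0.8, with a true difference of 0.50, gave mean estimates of 0.498 to 0.501 unadjusted and 0.500 to 0.502 for change from fasting. Neither is biased. Standard errors, unadjusted against change, were 0.287 and 0.411 at r = 0, 0.290 and 0.289 at r = 0.5, and 0.286 and 0.184 at r = 0.8. This agrees with the formulas.

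**What cannot be computed.** The share of the postprandial value that reflects overnight synthesis does not follow from anything in the documents.

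**The case against.** The strongest reply is that the plan is silent rather than wrong. A reader might infer that the outcome is the raw postprandial value and that fasting DNL will be discarded, but no sentence says so. The summaries in 4.11 are examples, and an iAUC or a time course that includes 0 min would bring the fasting value in. Section 4.9 also says the method follows the group's earlier work, which may settle the baseline handling but is not available here. This reply stands as far as it goes: the documents show an under-defined endpoint with no stated use of the fasting value, and not a decision to ignore it.

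Three further readings are tempting and are not supported.

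- *The lactose–maltodextrin contrast is biased by overnight label.* Drink order is randomised within person, the same evening labelling precedes every drink, and diet and activity are replicated beforehand. Overnight label is therefore equal across drinks in expectation.
- *With 24 people, chance imbalance in fasting DNL could manufacture an effect.* Visit-to-visit variation in fasting DNL is already part of the error term of a valid paired test, which keeps its nominal α with or without the covariate.
- *Label left from an earlier visit contaminates the result.* The evening pre-dose sample measures residual deuterium in body water. The documents give no basis for estimating label left in palmitate, and any such residue would follow visit order rather than drink.

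It is also fair to say that the gain may be small. At r = 0.3 the covariate is worth about two participants (26.4 against 24), and nothing in the documents excludes a lower r.

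**Conclusion.** The point holds as one of definition and efficiency. As written, 4.3 and 4.11 neither define the DNL summary and time point nor use the fasting DNL planned at each visit. The absolute postprandial level can include synthesis from before the drink, so it should not be read as a pure response to it. The randomised comparison remains valid.

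The possible gain from a fasting covariate is a variance reduction of 9% to 49% for r between 0.3 and 0.7, and close to nothing if r is near zero. It rests on an assumed r and, for the comparison with simple change, on equal within-person SDs. The change is still worth making: apart from one degree of freedom, the covariate does not lose precision at any r, and fixing the summary in advance closes a choice that is now open.

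**What to change.** 1. In 4.3, state the DNL summary and its time point. The 360 min value is one workable choice, since a blood sample is already scheduled then.
2. In 4.11, state that this summary is analysed in the within-person model with that visit's fasting (0 min) DNL as covariate. Fit participant as a fixed effect, or centre the fasting value within participant, so that the slope is the within-person one to which r refers.
3. Prefer the covariate to simple change from fasting, because r is unknown and change loses precision below r = 0.5.
4. Report fasting DNL by treatment and by period as a descriptive check.
5. Confirm that the VLDL fraction is prepared at 0 min and at the chosen time point. Sections 4.8 and 4.9 say only that a portion of plasma is ultracentrifuged, not which samples.

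The cost is protocol and SAP wording plus one degree of freedom: with 24 people and three drinks, the within-person residual falls from 23 × 2 = 46 to 45. No new blood draw is needed. If item 5 shows that VLDL is not being prepared at one of the two times, there would also be some laboratory work on samples already taken.

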## 4.4. Tertiary Outcomes

Treatment (lactose *versus* fructose *versus* maltodextrin) by sex (male *versus* female) interaction effect on:

- 1) Postprandial incremental area under the curve (iAUC) for plasma triglyceride concentrations (6-hour postprandial period).
- 2) Postprandial de novo lipogenesis (DNL)
- 3) Dietary fat oxidation
- 4) Postprandial iAUC for plasma insulin concentrations
- 5) Postprandial iAUC for plasma glucose concentrations
- 6) Postprandial iAUC for plasma galactose concentrations
- 7) Postprandial iAUC for plasma fructose concentrations
- 8) Postprandial iAUC for plasma VLDL-rich triglyceride [Svedberg flotation rate (Sf): 20-400] concentrations
- 9) Postprandial iAUC for plasma chylomicron-rich triglyceride (Sf: >400) concentrations
- 10) Postprandial iAUC for plasma lactate concentrations
- 11) Postprandial iAUC for plasma non-esterified fatty acid concentrations
- 12) Postprandial iAUC for plasma beta-hydroxybutyrate concentrations
- 13) Postprandial iAUC for plasma uric acid concentrations

#### 4.5. Participants and Eligibility Criteria

Twenty-four men (n = 12) and women (n = 12) will be recruited from the local area and matched for age and body mass index.

### **Inclusion Criteria:**

Age: 18-50 years and premenopausal (for women);

Body mass index: 18.5 – 40 kg·m^2

#### Exclusion criteria:

weight instability (>5 kg change in body mass within last 6 months)

diagnosis of any form of diabetes

intolerances or allergies to any of the study procedures (e.g. lactose intolerance)

Galactose disorders (e.g. galactokinase deficiency, UDPgalactose-4-epimerase deficiency, galactose-1-phosphate uridyl transferase deficiency)

Fructose malabsorption

Inborn errors of fructose metabolism (e.g. fructokinase deficiency, aldolase B deficiency, fructose-1,6-bisphosphatase deficiency)

pregnant or lactating

any condition that could introduce bias to the study (e.g. diagnoses of lipid disorders, including cardiovascular disease, or therapies that alter lipid or glucose metabolism, such as statins or niacin).

#### 4.6. Recruitment

Participants will be recruited through two different routes (1) direct advertisement and (2) letters sent to relevant patients in GP databases.

**Direct Advertisement:** Information about the study will be distributed via the placement of adverts and posters. Examples include: local newspapers and magazines; community noticeboards (e.g. in the public library, local market and cafes), community centres (e.g. leisure centres, churches, and art and music venues); larger local industry/establishments of employment (e.g. Wessex water and the University of Bath); healthcare centres (e.g. GP practices, pharmacies and dental clinics). In addition to printed adverts/posters, we will also utilise electronic routes: e.g. via E-mail bulletins, local community forums, university website/newsletters as well as social media (e.g. Twitter and Facebook). Potentially interested participants will be asked to contact the research team by email or phone if they want to find out more about the study. Potentially interested and eligible participants will be invited to a meeting to further discuss the study and what it entails. After reading the participant information sheets, if they decide to take part, they will be asked to sign an informed consent form.

Letters from GP database searches: Recruitment via this route will be conducted with the support of the Clinical Research Network (CRN) in BANES and Wiltshire. We will ask GP practices to search databases for patients who potentially meet the inclusion criteria. All patient identification and database searching will be conducted by the patient's existing care team (GPs, nurses and IT managers in study practices). Potentially eligible patients will be approached by a letter from their GP, jointly signed by the chief investigator. The recruitment letter will emphasise that participation is entirely voluntary and will not have any impact on their health care or their relationships with NHS staff.

Potentially interested participants will be asked to contact the research team via email or phone. Potentially interested and eligible participants will be invited to a meeting to further discuss the study and what it entails. After reading the participant information sheets, if they decide to take part, they

will be asked to sign an informed consent form. GP's will send out reminder letters to all eligible participants after two weeks, with an acknowledgement in the letter to ignore the reminder for those individuals who have already responded.

#### 4.7. Screening

Participants will be invited to the University of Bath to provide informed consent, and thereafter will be invited to undertake the assessments of eligibility listed below. Given the range of screening measurement required, these measurements may take place over more than one visit. As all potential participants will be offered feedback from the screening, in the event that a potential participant be deemed ineligible for the study based on a single measurement, the individual will be informed immediately and the subsequent screening measures will only be carried out at the participant's request.

**General health status:** Suitability to participate (e.g. menopausal status, pregnancy etc.) and other practical screening questions (e.g. any reason why participants could not complete the study within a reasonable time-frame etc.) will be self-reported by the participant via a health screen questionnaire. Food allergies and intolerances will be reported in this questionnaire to ensure that participants are able and willing to consume the test drinks.

**Anthropometrics:** Body mass will be measured using digital scales and height using a stadiometer. Body mass index (BMI) will be calculated by dividing body mass (kg) by height (m) squared. Waist circumference (cm) will be measured at the narrowest point between the lowest rib and iliac crest, and hip circumference (cm) will be measured at the widest point of the gluteal using a tape measure.

**Body composition (DXA):** The participant will be positioned supine in a dual-energy x-ray absorptiometry (DXA) scanner with their extremities within limits indicated and not touching their torso if possible. Fat mass (kg), lean mass (kg), body fat percentage (%) and bone mineral density (g/cm²) will be measured. Fat mass index will be calculated by dividing fat mass (kg) by height (m) squared.

### **Pre-trial standardisation**

To assist in producing a similar metabolic state on the morning of laboratory trial days, participants will be asked to record diet and physical activity for 48 h before the first trial, and to replicate these for the 48 h before each subsequent trial. Physical activity levels will be confirmed by objective measures using an Actiheart physical activity monitor (Cambridge Neurotechnology Ltd). This is attached to the chest either using ECG pads or a chest strap for measurement of free-living physical activity.

### Laboratory trial days

On the evening before trial days, a 5-mL blood sample will be taken (via venepuncture) for analysis of baseline H enrichment of the body water pool. Participants will then consume a standardised meal with 3 g·kg body water  of H2O for the assessment of fasting hepatic DNL. Participants will continue to consume H2O throughout trial days for the measurement of postprandial DNL.

On postprandial study days, participants will arrive at the laboratories in a rested, overnight fasted state, after 24-hours of diet and physical activity standardisation.

Body mass will first be recorded, and then a cannula will be inserted retrograde into a pre-heated dorsal hand vein for arterialised blood sampling, and baseline blood and expired breath samples will be taken for analysis of plasma metabolite and hormone concentrations, plasma tracer enrichments, and indirect calorimetry, respectively. Participants will then consume a high-fat test drink containing 50 g of fat, plus 100 g of either **lactose**, **sucrose or maltodextrin (Table 1)**. The test drink will also contain 200 mg [U-C]palmitate in order to trace the fate of the dietary fat. This quantity of lactose is roughly equivalent to 400 mL of milk and 400 g plain yoghurt, which is very high but not supraphysiological in light of typical UK intakes.

Table 1. Main laboratory trials and drink composition.

| Trial        | Carbohydrate type mixed with fat source (100 g)      | Fat Source
(50 g)                |
|--------------|--|-------------------------------------|
| Maltodextrin | Glucose polymer; a common sugar substitute (control) | 30 g palm oil and
20 g olive oil |
| Lactose      | Galactose-glucose disaccharide (intervention)        | 30 g palm oil and
20 g olive oil |
| Sucrose      | Fructose-glucose disaccharide (active comparator)    | 30 g palm oil and
20 g olive oil |

Low-calorie-sweetened chocolate flavouring will be added to all drinks.

Participants will be advised that dairy products are used in this study and people following a vegan diet may therefore choose not to participate.

Blood samples will be drawn at 30, 60, 120, 180, 240, 300 and 360 min after ingestion of the test drink and will be centrifuged for plasma collection and determination of metabolite and insulin concentrations (**Figure 4**). A portion of plasma will undergo density gradient ultracentrifugation to obtain the VLDL-rich [Svedberg flotation rate ( $S_f$ ): 20-400] and chylomicron-rich ( $S_f$ : >400) fractions. Expired breath samples will be taken at 60, 120, 180, 240, 300 and 360 min after ingestion for indirect calorimetry (Douglas bag method) and [ $^{13}$ C] appearance in expired CO2 (by isotope ratio mass spectrometry).

[figure not shown]

Figure 4. Schematic of the trial days

# 4.9. Measurements and Analysis

#### Plasma metabolite and hormone concentrations

Plasma concentrations of triglycerides, glucose, fructose, galactose, lactate, non-esterified fatty acids, glycerol, beta-hydroxybutyrate and uric acid concentrations will be determined by commercially-available enzymatic/colourimetric assays. Plasma insulin, estradiol and progesterone concentrations will be determined by commercially-available enzyme-linked, immunosorbent assays. A portion of plasma will undergo density gradient ultracentrifugation to obtain the VLDL-rich [Svedberg flotation rate ( $S_f$ ): 20-400] and chylomicron-rich ( $S_f$ : >400) fractions.

#### Fasting and postprandial *de novo* lipogenesis

S

Postprandial DNL will be determined by the incorporation of deuterium from  $^2H_2O$  in plasma water into VLDL-TG palmitate using gas chromatography-mass spectrometry (Finnigan GasBench II Thermo Fisher Scientific, Paisley, U.K.) with monitoring ions with mass-to-charge ratios of 270 (M+0) and 271 (M+1) as we have previously performed. In this respect, DNL refers to the proportion of newly synthesized palmitate in VLDL-TG, and this represents the synthesis of fatty acids from non-lipid precursors. The benefit of this method over tracing labelled lactose is that labelling the ingested sugar only captures the conversion of that specific precursor to fatty acids. The  $^2H_2O$  method on the other hand, captures DNL from all precursors. Therefore, if lactose ingestion stimulates the conversion of lactate, galactose and glucose to lipid, this would be captured by our proposed method, but would be partially missed if using lactose labelling.

#### Substrate oxidation

Whole-body carbohydrate and fat utilisation rates will be determined in the fasted and postprandial state using indirect calorimetry (10-min samples every 60 minutes). Dietary fat oxidation will be determined by the appearance of [¹³C] in breath CO₂ in line with our previous work(²²²). Specifically, ¹³C-to-¹²C ratios in breath samples, and the relative rate of whole-body meal-derived fat oxidation will be calculated. First, the rate of expiration of ¹³CO₂ in breath will be calculated by multiplying CO₂ production rate as determined by indirect calorimetry (mmol·min⁻¹), by the expired CO₂

enrichment of C (tracer-to-tracee ratio). To allow for sequestration of label into the bicarbonate pool, a dietary acetate recovery factor of 51% will be applied, and data will be corrected for fat-free mass as determined by DXA.

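### Section 4.9 describes no drink-specific 13C background for dietary fat oxidation, so the lactose versus maltodextrin contrast can be biased by the carbohydrate itself

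*Combined protocol and SAP*

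**What the plan says.** Dietary fat oxidation is the second of two secondary outcomes. Section 4.3 lists it as "Dietary fat oxidation, using a stable isotope-labelled palmitate" and sets the contrast as "The effect of treatment (lactose versus maltodextrin co-ingestion on" each outcome. It returns in section 4.4 as a three-drink, treatment-by-sex outcome, and it is research objective 3 in section 3.

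Under Laboratory trial days (section 4.8), each drink is described as "containing 50 g of fat, plus 100 g of either" lactose, sucrose or maltodextrin. The tracer is the same in all three: "The test drink will also contain 200 mg" of uniformly 13C-labelled palmitate. Before the drink, "baseline blood and expired breath samples will be taken for analysis". Breath is then collected hourly from 60 to 360 minutes.

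Under Substrate oxidation (section 4.9), "Dietary fat oxidation will be determined by the appearance of" 13C in breath CO2. The calculation is CO2 production rate multiplied by breath 13C enrichment, expressed as a tracer-to-tracee ratio. Two adjustments are named: a 51% acetate recovery factor, with no variation by drink, and fat-free mass. The section also refers to the group's earlier work (reference 22) for the method. The protocol does not give the botanical source or natural 13C content of any of the three carbohydrates, a plan to measure it, an unlabelled control drink, or a background that depends on the drink.

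**The concern.** Breath 13CO2 after the drink comes from two places: the labelled palmitate, and the natural 13C in everything else being oxidised. The largest new fuel after the drink is the 100 g of carbohydrate, and that is exactly what is randomised. If the lactose and the maltodextrin differ in natural 13C, breath enrichment will differ between the two visits even when dietary fat oxidation is the same.

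The design does not remove this. Randomisation and the crossover balance participant and period effects, but this shift belongs to the drink. Subtracting the fasting sample removes the pre-drink background only. The 51% factor rescales the artefact together with the signal. What is at stake is the answer to research objective 3: an apparent suppression of dietary fat oxidation, or an apparent lack of one, could come partly from the ingredients.

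**Working it through.** **Plan's own figure.** The plan gives no expected value or precision for dietary fat oxidation. Its one design figure, power 0.94 with 24 participants and d = 0.75 (section 4.10), concerns triglycerides. A two-sided paired t-test at 0.05 with noncentrality 0.75 x sqrt(24) = 3.67 and 23 degrees of freedom gives 0.9403, so it reproduces, but it does not bear on this point.

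**Inputs from the protocol.** 200 mg tracer; 100 g carbohydrate per drink; recovery factor 0.51.

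**Assumptions, not in the protocol.** Difference in natural 13C between the two carbohydrates, 0-15 per mil; share of the 100 g oxidised to breath CO2 in 6 h, 30-70%; share of label reaching breath, 10-20%; reference 13C ratio 0.0112.

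**Step 1, tracer.** 0.200 g / 272.5 g/mol x 16 carbons = 11.74 mmol 13C. With 10-20% in breath, the signal is 1.17-2.35 mmol.

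**Step 2, carbohydrate carbon.**
- Glucose polymer: 100/162.14 x 6 = 3.70 mol.
- Anhydrous lactose or sucrose: 100/342.30 x 12 = 3.51 mol.
- Lactose monohydrate: 100/360.31 x 12 = 3.33 mol.

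At natural abundance this is about 37-41 mmol 13C, or 3.1-3.5 times the tracer's 13C. Small differences in abundance can therefore matter.

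**Step 3, carbohydrates that differ in natural 13C.** Extra breath 13C = 3.6 mol x fraction oxidised x 0.0112 x (per mil difference / 1000). For 5 per mil and 30% oxidised: 3.6 x 0.30 x 0.0112 x 0.005 = 0.060 mmol. For 15 per mil and 70%: 3.6 x 0.70 x 0.0112 x 0.015 = 0.42 mmol.

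| Difference | Extra 13C (30-70% oxidised) | Share of tracer signal | Share if carbohydrate CO2 also has 51% recovery |
|---|---|---|---|
| 0 per mil | 0 | 0 | 0 |
| 5 per mil | 0.06-0.14 mmol | 3-12% | 1-6% |
| 15 per mil | 0.18-0.42 mmol | 8-36% | 4-18% |

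The third column divides the smaller amount by 2.35 mmol and the larger by 1.17 mmol. The last column multiplies the numerator by 0.51, to put it on the same footing as label measured in breath.

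**Step 4, same natural 13C, different oxidation.** Suppose both carbohydrates sit 5-15 per mil above fasting breath and the share oxidised differs by 10-20 percentage points (assumed). Then 3.51 x 0.10 x 0.0112 x 0.005 = 0.020 mmol, rising to 3.51 x 0.20 x 0.0112 x 0.015 = 0.118 mmol. Dividing by 0.51 x 11.74 = 5.99 mmol gives 0.3-2.0 percentage points of the tracer dose. A zero difference between products therefore gives no error only if they are also oxidised alike or match fasting breath.

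**Step 5, effect on the test.** With 24 participants, a pure bias of 0.2, 0.3 or 0.5 SD of the paired difference raises the two-sided 5% false-positive rate to 16%, 29% or 65%. The protocol gives no SD for this outcome, so the amounts above cannot be converted to that scale.

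**The case against.** The strongest objection is that section 4.9 points to an earlier published method and gives only a short account of it, opening with a first step and numbering no second. A background correction may exist there. Tracer-to-tracee ratio also normally implies that some background is subtracted, and a fasting breath sample is available for it. This stands in part: a reader might infer that the trial applies no correction at all, and the documents do not support that. They support only that none is described. But a fasting background, even if subtracted, does not deal with a shift that begins after the drink.

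A second objection is that size and direction are assumed. This stands in full. A reader might infer that the bias favours the hypothesis that lactose suppresses dietary fat oxidation. That holds only if the maltodextrin is the richer in 13C; the reverse would hide a true suppression, and the protocol gives no sourcing to choose between them. A reader might also infer a very large error: with 5% of label in breath, 0.42 / (0.05 x 11.74) = 72%. That needs three extreme assumptions at once and counts carbohydrate-derived CO2 in full against label already reduced by sequestration.

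Third, subtracting a carbohydrate background can bring in its own bias. Calorimetry measures total carbohydrate oxidation, including glycogen, and the trial expects the sugars to alter de novo lipogenesis, which affects calorimetric estimates. This also stands, and it is why the correction belongs in a bounded sensitivity analysis and should not replace the uncorrected result.

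**Conclusion.** The concern holds in a limited form. The calculation written in section 4.9 leaves the lactose versus maltodextrin contrast in dietary fat oxidation, and the three-arm tertiary analyses, open to a treatment-aligned bias. There are two routes: a difference in natural 13C between the carbohydrates, or a shared abundance away from fasting breath combined with unequal oxidation. Under the stated assumptions the first route gives an error from about nil to about 36% of the tracer signal, roughly half that if carbohydrate-derived CO2 has the same 51% recovery. The direction is unknown. Neither the triglyceride primary outcome nor de novo lipogenesis measured with deuterium is affected. If the cited method already includes a drink-specific background, stating it in section 4.9 would largely settle the point. This is a cheap improvement and not a flaw in the trial's main comparison.

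**What to change.** In section 4.8, state the source of each carbohydrate, match their natural 13C where products allow, and assay each batch on the isotope-ratio mass spectrometer already planned for breath. Matching alone is not enough unless the abundance also matches fasting breath (step 4 of the working).

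In section 4.9, state how the fasting sample is used and pre-specify a drink-specific background: carbohydrate oxidation from the planned calorimetry x assumed share coming from the drink x measured 13C excess of that carbohydrate over fasting breath x CO2 recovery, with recovery on the same scale as for the tracer. Subtract this before the 51% factor is applied. Report dietary fat oxidation with and without it. Because calorimetry cannot separate drink from endogenous carbohydrate, treat full subtraction as the upper bound and vary the assumed share below it.

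The cost is a sourcing check, a few extra assays and one more line in the calculation, with no added participant procedure. The downside is that the corrected result depends on assumptions, so it should be read as a range.
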